# 8.9. Discontinuation from follow-up

If a patient withdraws from further follow-up the change of participation status form should be submitted to ICR-CTSU . Sites should report whether the patient simply no longer wishes to attend trial follow up visits or any other aspect of the trial (eg substudies), or whether the patient has withdrawn consent for any further information to be sent to the ICR-CTSU.

RE-ARM protocol IRAS 280335 / CCR5167

# 8.10. Schedule of assessments

Time point					 					_
(all cycle numbers relate to on-trial atezolizumab)	_				oint		<del></del>	   <del>-</del>   -	n of ost 1 (to	o u
Activity	Screening 	Cycle 1	Cycle 2	Cycle 3	Week 9 (Primary endpoint)	Cycle 4	Cycle 5 - 34	RECIST v1.1 progression	Continuation of treatment post RECIST v1.1 progression (to cycle 34)	Discontinuation of treatment
Written informed consent	Х									
Confirmation of eligibility	Χ									
Medical history	Χ									
Assessment of ECOG PS	Χ									
Serology (HIV, hepatitis B, hepatitis C) (within 12 months prior to randomisation)	Χ									
Clinical assessment - physical exam 	Χ	Х	Х	Χ		Χ	Х	Х	Х	
FBC, U&E, amylase, LFTs 	Χ	Х	Х	Χ		Χ	Х	Х	Х	
Thyroid function tests 	Χ	Х		Χ			X 		X 	
Concomitant medication assessment 	Χ	Х	Х	Χ		Χ	X		Х	
Adverse event assessment (CTCAE v5) 	Χ	Х	Х	Χ		Χ	Х		X	X 
CT chest, abdomen, pelvis assessed with RECIST v1.1 	Χ				Х		X 			
CT chest, abdomen, pelvis assessed with iRECIST 									X 	
RT to single metastasis (if allocated)		Х								
Intravenous atezolizumab (day 1)		Χ	Χ	Х		Χ	Х		Х	
Stop atezolizumab										Χ
Disease status and survival										X 

#### Footnotes

- 1. Within 28 days before randomisation unless otherwise stated.
- 2. Assessments should be conducted within 72 hours prior to day one of each three-weekly cycle. Following screening, physical examinations should be conducted as clinically indicated.
- 3. To include Hb, Plt, WBC, creatinine, sodium, potassium, ALP, AST or ALT, bilirubin and amylase as a minimum.

RE-ARM protocol IRAS 280335 / CCR5167

4. CT CAP with RECIST v1.1 or iRECIST assessment as appropriate should be conducted at the expected time point irrespective of any delays to atezolizumab administration. The planned site of radiotherapy should not be used for RECIST v1.1 or iRECIST assessment (as either a target or non-target lesion), but measurement of this lesion should be recorded on the dedicated eCRF where required.

- 5. Thyroid function assessments should be conducted every 6 weeks.
- 6. CT CAP with RECIST v1.1 assessment should be conducted every 9 weeks within the first year, every 12 weeks within the second year for those patients continuing treatment. See appendix A4.
- 7. Upon RECIST v1.1 assessment of PD, for patients continuing treatment, CT CAP should be conducted with iRECIST assessment 6 weeks later, then 12 weeks later for those patients without iCPD and continuing treatment. Following this CT CAP with iRECIST assessment should continue every 9 weeks within the first year of study treatment and every 12 weeks within the second year until iCPD or discontinuation of treatment. See appendix A4.
- 8. Assessment of immune related toxicities up to 90 days post treatment completion (prior to initiation of any further treatment).
- 9. Disease status and survival should be assessed every 3 months post atezolizumab discontinuation up to two years after the start of study treatment, then every 6 months thereafter

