#### 5.3. Inclusion criteria

- 1. Histologically confirmed metastatic urothelial carcinoma not amenable to curative treatment with surgery or radiotherapy. Mixed histology is permitted if predominantly TCC.
- 2. Received a minimum of 3 cycles and maximum of 6 cycles of open label atezolizumab treatment\* (either first, second or third line¥) with an overall best response of stable disease according to local investigator assessment.
- 3. At least one extra-cranial metastatic site suitable for radiotherapy (see section 9.1).
- 4. At least one RECIST v1.1 measurable lesion distant to the planned site of radiotherapy.
- 5. No radiotherapy within four weeks prior to starting pre-study atezolizumab or during atezolizumab treatment.
- 6. Satisfactory haematological and biochemical profile (Hb >90 g/L, Plt>100 x  $10^9$ /L, WBC > 3.0 x  $10^9$ /L, creatinine < 1.5 ULN, AST or ALT <3X ULN, bilirubin <1.5x ULN).
- 7. ECOG PS 0-1.
- 8. Age ≥18 years.
- 9. Written informed consent.
- \* In accordance with therapeutic indications as stated in the current summary of product characteristics
- Neoadjuvant treatment received more than a year prior to trial entry will not be considered a line of treatment.

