#### 8. TRIAL ASSESSMENTS

## 8.1. Screening assessments

The following assessments should be conducted within 28 days prior to randomisation unless otherwise indicated:

- Physical examination
- Medical history
- ECOG performance status assessment
- Full blood count, urea and electrolytes, amylase and liver function assessment
- Thyroid function assessment
- Serology (HIV, hepatitis B, hepatitis C) (within 12 months prior to randomisation)
- Concomitant medication assessment
- Adverse event assessment (CTCAE v5)
- CT chest abdomen pelvis (CAP) and RECIST v1.1 assessment\*
- QoL sub-study questionnaire (if participating): EORTC QLQ-C30 and EQ-5D-5L

\*The planned site of radiotherapy should not be used for RECIST v1.1 assessment (as either a target or non-target lesion), but measurement of this lesion should be recorded on the dedicated eCRF.

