#### 8.3. On-treatment assessments

Patients will receive study atezolizumab 1200mg IV three weekly until loss of clinical benefit or unmanageable toxicity. If allocated, radiotherapy should start on the same day as the first cycle of study atezolizumab if possible. For further details see section 9 – Trial Treatment.

The following assessments should be conducted before each three-weekly cycle of atezolizumab (within 72 hrs prior to day 1):

- Physical examination as clinically indicated
- Full blood count, urea and electrolytes, amylase, liver function assessment
- Concomitant medication assessment
- Adverse event assessment (CTCAE v5)

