#### Every six weeks:

• Thyroid function (every 6 weeks) - results do not need to be available on day 1

Translational sub-study sample schedule (if participating):

- RT patients only at fraction 4 or 5 EDTA 10ml x 3 and Tempus 3ml
- Week 3 from start of study atezolizumab EDTA 10ml x 3 and Tempus 3ml
- Week 9 from start of study atezolizumab (primary endpoint) EDTA 10ml x 3, Tempus 3ml and Streck 10ml

Quality of life sub-study questionnaire schedule - EORTC QLQ-C30 and EQ-5D-5L (if participating):

- Week 9
- Six months
- Any participants still receiving atezolizumab at 12 months

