# 9.2.5. Supportive care

Supportive care should be given in accordance with the current summary of product characteristics and local policy.

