#### 9.2.8. Dose modifications – atezolizumab

Atezolizumab dose reductions are not recommended. Recommended treatment modifications in the case of adverse reactions are detailed below.

Immune related adverse reaction	Severity (NCICTCAE v5)	Treatment modification
Pneumonitis	Grade 1	Consider treatment delay, monitor every 2-3 days
	Grade 2	Withhold atezolizumab
		Treatment may be resumed when the event improves to Grade 0 or Grade 1 within 12 weeks, and corticosteroids have been reduced to ≤ 10 mg prednisolone or equivalent per day
	Grade 3 or 4	Permanently discontinue atezolizumab
Hepatitis	Grade 2:	Withhold atezolizumab

Immune related adverse reaction	Severity (NCICTCAE v5)	Treatment modification
	(ALT or AST > 3 to 5 x upper limit of normal [ULN] or blood bilirubin > 1.5 to 3 x ULN)	Treatment may be resumed when the event improves to Grade 0 or Grade 1 within 12 weeks and corticosteroids have been reduced to ≤ 10 mg prednisolone or equivalent per day
	Grade 3 or 4:	Permanently discontinue atezolizumab
	(ALT or AST > 5 x ULN	Consider hepatology referral
	or	
	blood bilirubin > 3 x ULN)	
Colitis	Grade 2 or 3 diarrhoea	Withhold atezolizumab
	<pre>(increase of ≥ 4 stools/day over baseline) or Symptomatic colitis</pre>	Treatment may be resumed when the event improves to Grade 0 or Grade 1 within 12 weeks and corticosteroids have been reduced to ≤ 10 mg prednisolone or equivalent per day  Consider gastroenterology referral
	Grade 4 diarrhoea or colitis (life threatening; urgent intervention indicated)	Permanently discontinue atezolizumab
Hypothyroidism or	Symptomatic	Withhold atezolizumab
hyperthyroidism		Hypothyroidism:
		Treatment may be resumed when symptoms are controlled by thyroid replacement therapy and TSH levels are decreasing
		Hyperthyroidism:
		Treatment may be resumed when symptoms are controlled by anti-thyroid medicinal product and thyroid function is improving
		Consider endocrinology referral
Adrenal insufficiency	Symptomatic	Withhold atezolizumab
		Treatment may be resumed when the symptoms improve to Grade 0 or Grade 1 within 12 weeks and corticosteroids have been reduced to ≤ 10 mg prednisolone or equivalent per day and patient is stable on replacement therapy
		Consider endocrinology referral

Immune related adverse reaction	Severity (NCICTCAE v5)	Treatment modification		
Hypophysitis	Grade 2 or 3	Withhold atezolizumab		

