		Treatment may be resumed when the symptoms improve to Grade 0 or Grade 1 within 12 weeks and corticosteroids have been reduced to ≤ 10 mg prednisolone or equivalent per day and patient is stable on replacement therapy		
		Consider endocrinology referral		
	Grade 4	Permanently discontinue atezolizumab		
Type 1 diabetes	Grade 3 or 4 hyperglycaemia	Withhold atezolizumab		
mellitus	(fasting glucose > 250 mg/dL or 13.9 mmol/L)	Treatment may be resumed when metabolic control is achieved on insulin replacement therapy		
Infusion-related reactions	Grade 1 or 2	Reduce infusion rate or interrupt. Premedication with antipyretic and antihistamines may be considered.		
		Treatment may be resumed when the event is resolved		
	Grade 3 or 4	Permanently discontinue atezolizumab		
Rash	Grade 3	Withhold atezolizumab		
		Treatment may be resumed when rash is resolved and corticosteroids have been		
		reduced to ≤ 10 mg prednisolone or		
		equivalent per day		
	Grade 4	Permanently discontinue atezolizumab		
Myasthenic syndrome/myasthenia gravis, Guillain-Barré syndrome and Meningoencephalitis	All grades	Permanently discontinue atezolizumab		
Pancreatitis	Grade 3 or 4 serum amylase	Withhold atezolizumab		
	or lipase levels increased (> 2 x ULN)  or  Grade 2 or 3 pancreatitis	Treatment may be resumed when serum amylase and lipase levels improve to Grade 0 or Grade 1 within 12 weeks, or symptoms of pancreatitis have resolved, and corticosteroids have been reduced to ≤ 10 mg prednisolone or equivalent per day		

Immune related adverse reaction	Severity (NCICTCAE v5)	Treatment modification
	Grade 4 or any grade of recurrent pancreatitis	Permanently discontinue atezolizumab
Myocarditis	Grade 2	Withhold atezolizumab
		Treatment may be resumed when the symptoms improve to Grade 0 or Grade 1 within 12 weeks and corticosteroids have been reduced to ≤ 10 mg prednisolone or equivalent per cay
	Grade 3 and 4	Permanently discontinue atezolizumab
Nephritis	Grade 2:	Withhold atezolizumab
	(creatinine level > 1.5 to 3.0 x baseline or > 1.5 to 3.0 x ULN)	Treatment may be resumed when the event improves to Grade 0 or Grade 1 within 12 weeks and corticosteroids have been reduced to ≤ 10 mg prednisolone or equivalent per day
	Grade 3 or 4:	Permanently discontinue atezolizumab
	(creatinine level > 3.0 x baseline or > 3.0 x	,
Myositis	Grade 2 or 3	Withhold atezolizumab
	Grade 4 or grade 3 recurrent myositis	Permanently discontinue atezolizumab

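### Section 9.2.8 recommends withholding atezolizumab above a fasting glucose of 13.9 mmol/L, but no scheduled blood panel includes glucose

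*Protocol*

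**What the plan says.** Section 9.2.8 of the protocol introduces its table with "Recommended treatment modifications in the case of adverse reactions are detailed below". The type 1 diabetes row has a single severity criterion, Grade 3 or 4 hyperglycaemia, defined as "fasting glucose > 250 mg/dL or 13.9 mmol/L". The action is to withhold atezolizumab; dosing may restart once the patient is metabolically controlled on insulin.

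The scheduled safety bloods are:

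- **Screening (8.1):** "Full blood count, urea and electrolytes, amylase and liver function assessment", with thyroid function and viral serology listed separately.
- **Before each cycle (8.3):** "Full blood count, urea and electrolytes, amylase, liver function assessment". The same list is used at RECIST v1.1 progression for patients who stop treatment (8.7).
- **Every six weeks (8.3):** "Thyroid function (every 6 weeks) - results do not need to be available on day 1".
- **Minimum content of the panel (8.10, footnote 3):** "To include Hb, Plt, WBC, creatinine, sodium, potassium, ALP, AST or ALT, bilirubin and amylase as a minimum".

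The trial schema and the sub-study schedule (8.10.1) do not add glucose. In the protocol as shown, it appears only in the 9.2.8 row.

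**The concern.** The diabetes criterion is a laboratory value, so a patient without symptoms can be recognised as meeting it only by a blood test. The schedule requires no such test. A site could do everything asked of it and still give the next infusion to someone already above the level at which the protocol recommends withholding.

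The sponsor recognises the risk: immune-related diabetes mellitus is an adverse event of special interest (11.1.4). There is also no scheduled baseline glucose. Patients with type 1 diabetes may enter, and low-dose corticosteroids are allowed at entry (5.4). Systemic corticosteroids may be used on study to treat immune-related reactions (9.2.6). A raised value found later in such a patient would have no trial reference point against which to judge it.

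What is at stake is individual patient safety. No bias between arms is suggested.

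**Working it through.** No sample size, power or error rate enters this point. The check compares the triggers in 9.2.8 with the scheduled tests and then counts the panels.

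**1. The threshold itself.** Dividing mg/dL by 18.016 gives mmol/L: 250 / 18.016 = 13.88, which rounds to 13.9. The two stated units agree, and the threshold is not in question.

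**2. Rows of 9.2.8 with a numeric laboratory threshold, against footnote 3.**

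| Row of 9.2.8 | Trigger analytes | In footnote 3? |
|---|---|---|
| Hepatitis | ALT or AST, bilirubin | Yes |
| Nephritis | Creatinine | Yes |
| Pancreatitis | Amylase or lipase | Amylase yes, lipase no |
| Type 1 diabetes | Fasting glucose | No |

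Three of the four rows have at least one scheduled trigger analyte. Diabetes has none.

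**3. Two comparisons within the protocol.** The pancreatitis row lists raised enzymes as a trigger separate from clinical pancreatitis, so the table does act on laboratory values alone, and amylase is drawn before every cycle. Thyroid function is scheduled every six weeks although the thyroid row is triggered by symptoms. The protocol therefore schedules a test where its table relies on symptoms, and omits one where its table relies on a laboratory value.

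**4. Number of panels.** From the blood-count and biochemistry row of the 8.10 table:

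- screening: 1
- pre-cycle: up to 34
- RECIST v1.1 progression: 1
- total: 1 + 34 + 1 = up to 36 per patient, of which 0 require glucose

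This is an upper bound. Many patients will stop before cycle 34, and the progression panel may coincide with a pre-cycle one. If all 102 planned patients completed every panel, adding glucose throughout would mean 36 × 102 = 3,672 tests.

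**5. What cannot be computed.** The protocol gives neither a rate of immune-related diabetes nor the share of cases without symptoms, so no probability of a missed case is offered.

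**The case against.** The strongest reply is that nothing here is contradictory. The table in 9.2.8 gives recommendations once a reaction has been identified; it is not a rule for releasing each dose. On that reading the glucose figure grades a diabetes already diagnosed. Section 11.2 points the same way, since out-of-range laboratory values count as adverse events only when clinically relevant. Footnote 3 sets a floor, so sites may test glucose. Section 9.2.5 adds "Supportive care should be given in accordance with the current summary of product characteristics and local policy". An adverse event assessment precedes each cycle, and diabetes is already flagged for rapid reporting. Other rows, such as adrenal insufficiency and myocarditis, also have no dedicated test, so the one-in-four count depends on restricting it to numeric thresholds. Prior exposure matters too: entry requires "Received a minimum of 3 cycles and maximum of 6 cycles of open label atezolizumab treatment", so some cases will have surfaced before randomisation. Finally, random samples set against a fasting threshold will produce false alarms.

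Much of this stands as a limit on size. The protocol does not contradict itself, symptomatic cases would still be found, and the exposed group is narrow: patients without symptoms whose fasting glucose is above the threshold. The panel counts measure testing, not risk. A progression panel in a patient who is stopping treatment cannot prevent a further infusion.

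It does not remove the gap. Section 11.2 governs what is reported, not when a dose is withheld. The floor in footnote 3 and the sentence in 9.2.5 permit a glucose test without requiring one, and 9.2.5 concerns supportive care. A clinical assessment cannot see a rise that causes no symptoms. Rows triggered by symptoms or clinical grade are reasonably left to clinical assessment; a row whose only criterion is a laboratory value is not.

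**Conclusion.** The point holds. The protocol states a glucose level at which atezolizumab should be withheld and schedules no test that could show it. Diabetes is the only one of the four rows with a numeric laboratory threshold that has no trigger analyte in the minimum panel, and glucose is required in 0 of up to 36 panels per patient.

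The gap is small and confined to safety monitoring. The primary endpoint, sample size and error rates are unaffected. The conclusion assumes a site that follows the written schedule and adds nothing. Where local policy already includes glucose the gap closes in practice, but the protocol does not ensure this. The number of patients who would benefit is probably small and cannot be estimated from the document.

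**What to change.** Add glucose to footnote 3 of 8.10 and to the lists in 8.1 and 8.3, measured on the blood already taken at screening and in the 72 hours before each cycle. A random sample is acceptable. Then state the following:

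- If a random value exceeds 13.9 mmol/L, a prompt fasting sample is taken and the investigator reviews it before the due dose.
- If the fasting value confirms it, the diabetes row of 9.2.8 applies. If not, the dose goes ahead.
- In patients with known diabetes or on corticosteroids, the value is judged against the screening result and the clinical context before it is attributed to immune-related diabetes.

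The threshold and the restart rule stay as they are.

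The cost is amendment wording and one analyte on existing draws: at most 36 per patient, fewer for those who stop early, with no extra routine visit. The downsides are a small laboratory cost, fasting repeats for some raised random values (mainly in patients with diabetes or on corticosteroids) and an occasional short dose delay.

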# 8.10.1. Sub-study schedule of assessments

Time point (all week/month numbers relate to the start of on-trial atezolizumab)  Activity	Screening	Baseline – post randomisation	Fraction 4 or 5 of RT (RT group only)	Week 3	Week 9 (Primary endpoint)	RECIST v1.1 progression	6 months	12 months
Translational sub-study sample acquisition schedule								
Blood: EDTA 10ml x 3, Tempus 3ml		Х	Х	Χ	Х	X 		
Blood: Streck 10ml		Х			Х	X 		
Access to FFPE blocks from diagnostic procedures 								
Quality of Life (QoL) sub-study schedule								
EORTC QLQ-C30 and EQ-5D-5L	X 				Х		Χ	X 

#### **Footnotes**

- 1. Blood samples to be taken at RECIST v1.1 progression (if this did not occur at 9 weeks).
- 2. Within 28 days before randomisation.
- 3. QoL to be assessed at 6 months for all sub-study patients and 12 months for all sub-study patients who are still being treated with atezolizumab.
- 4. FFPE tumour tissue samples will be requested retrospectively and should not be sent without the prior notice of ICR- CTSU.

#### 9. TRIAL TREATMENT

All participants will receive atezolizumab, the investigational medicinal product within RE-ARM. Participants in the atezolizumab plus radiotherapy group will also receive radiotherapy to the primary site or a metastatic lesion.

## 9.1. Radiotherapy

Patients randomised to radiotherapy will receive radiotherapy to the primary site or a pre-specified metastatic lesion. The planned site of radiotherapy must be specified at trial entry (prior to randomisation) and this lesion must not be used for RECIST assessment, whether or not the patient is allocated to receive radiotherapy. Radiotherapy treatment guidelines are provided below. Any queries regarding radiotherapy requirements should be directed to the RE-ARM trial manager.

## 9.1.1. Radiotherapy target selection

It is recommended that the lesion selected to receive radiotherapy:

- Should be a lesion that is progressing, if applicable
- May be RECIST v1.1 measurable or non-measurable e.g. bone or bladder
- Should be 1.5cm to 10cm in diameter. If not available a larger lesion can be selected and partially treated
- Should not have been previously irradiated

## 9.1.2. Radiotherapy treatment timelines

Radiotherapy should preferably be started on the first day of the first cycle of on study atezolizumab but, if this is not feasible, should be started as soon as possible after the first on study atezolizumab dose and completed before the second on study cycle commences.

The RE-ARM trial manager should be contacted for advice if problems are anticipated achieving the radiotherapy treatment timelines provided at randomisation for any participant.

# 9.1.3. Radiotherapy treatment technique

The radiotherapy dose will be 20Gy in 5 fractions to be delivered over 1 week.

Treatment can start on any day of the week.

The treatment technique will be as per normal clinical practice with the aim of delivering treatment with minimal toxicity. Conformal or IMRT/VMAT delivery will be preferred but less complex fields will be accepted e.g. single fields to spinal vertebrae.

#### 9.1.4. Target volume definition

The Clinical Target Volume (CTV) will be the investigator defined gross tumour volume (GTV) plus 0.5 cm. An additional 0.5 - 1.0cm margin will be added to the CTV to form the planning target volume (PTV). The PTV should have a minimum diameter of 3.5 cm and not exceed a maximum diameter of 12 cm. The treated target site may be RECIST measurable or non-measurable.

Ideally, the whole lesion will be irradiated however partial irradiation is permitted in order not to exceed the maximum allowable PTV.

#### 9.1.5. Dose volume constraints

The dose to the measured lesion(s) used for RECIST assessment should be <4Gy (20% of target dose). The maximum and median dose to the measured lesion will be recorded (if within 10cm of the irradiated lesion or within the encompass of one or more beams). Any lesion which receives 4Gy or more should not be used for RECIST reporting.

